9.2 Case Report Form Completion

The eCRF will be presented in an electronic casebook comprising a series of electronic forms. The Subject Number should always be indicated and date (and time, if applicable) of each assessment should be entered in the eCRF.

The eCRFs must be completed in timely manner so that this does not delay the ongoing data validation, review, and quality control. The final, completed eCRF for each subject must be signed and dated by the Investigator on the appropriate eCRF form to signify that he/she has reviewed the casebook and certifies it to be complete and accurate.

The eCRF will feature a special means for correcting errors in the previously entered data. A complete audit trail of the original entries, changes and deletions, session dates and times, and the credentials of the eCRF user who performed the operation will be maintained by the system.

9.3 Data Processing

The data collected on the eCRFs will be captured in a specially constructed and validated database. The data will be validated using both manual and electronic means. Clarification of data will be requested from the Investigator site as required. An audit trail of the original database entries, changes and deletions, session dates and times, and the credentials of the database user who performed the operation will be maintained by the system. The completed database will be quality assured and locked to prevent further changes. A full database extract, including sunlight exposure diary data, will be made available for statistical analysis according to the methods outlined in Section 10 and the Statistical Analysis Plan (SAP).

AEs and medical history entries will be coded using the Medical Dictionary for Regulatory Activities (MedDRA). Concomitant medications will be coded using the World Health Organization (WHO) Medication Dictionary. Versions of the dictionaries used will be documented in the Data Management Plan and SAP.

10. STATISTICAL METHODS AND PLANNED ANALYSES

This section provides the basis for the statistical analysis plan (SAP) for the study. The SAP may be revised during the study to accommodate amendments to the clinical study protocol and to make changes to adapt to unexpected issues in study execution and data that may affect planned analyses.

10.1 Sample Size Consideration:

The sample size for this study is not based on a formal statistical calculation since this is a clinical study for a rare disease. However, a sample size of 34 subjects per treatment group is considered to be adequate to meet the objectives of the study.

10.1.1 Analysis Populations

- Safety population: includes all randomized subjects who received at least 1 dose of study medication.
- Intent-to-treat (ITT) population: includes all randomized subjects who received at least 1 dose of study medication and who have at least 1 post-baseline efficacy assessment.
- Per-protocol (PP) population: includes all ITT subjects who do not have any major protocol violations and complete Week 16 (the end of double-blinded treatment period).
- PK population: includes all randomized subjects who receive at least 1 dose of study medication and who have at least 1 post-dose value of plasma concentration time point to be included in the PK analysis without important protocol deviations which may affect the PK of study medication.

10.2 Statistical Methods

A SAP containing details of all the analyses and outputs will be prepared and approved before the study database lock. The ITT population will be used for all efficacy analyses. All safety analysis will be performed on the Safety population and PK assessments will be performed on the PK population.

Unless otherwise specified, the baseline values will be the last non-missing value before receiving the first dose of study medication.

Baseline for an efficacy endpoint based on sunlight exposure time will be the mean of the daily value of the endpoint in a 14-day window before Day 1. Similarly, for this endpoint, their values at each post baseline visits/time-points (Weeks 2, 4, 6, 8, 10, 12, 14, 16, and 22) are the mean of the daily value of the endpoint in a 14-day window on or before the visit.

Continuous endpoints will be summarized with the descriptive statistics (the number of observations, mean, standard deviation (SD), median, minimum, and maximum). Categorical endpoints will be summarized using frequency counts and percentages.

All statistical tests will be 2-sided with 5% significance level. Point estimates of treatment differences will be provided using 2-sided 95% confidence intervals (CIs), where

applicable.

10.2.1 Demographic and Other Baseline Characteristics

Baseline demographic such as age, sex, body weight, body mass index, ethnicity and race, and other baseline characteristics such as will be summarized by treatment group using descriptive statistics on the ITT population.

10.2.2 Efficacy Assessments

10.2.2.1 Analysis of Primary Efficacy Endpoints

The primary treatment comparisons of interest are the change from baseline in average daily time (**minutes**) to first prodromal symptom associated with sunlight exposure between 1 hour post sunrise and 1 hour pre-sunset for the two MT 7117 doses (■, and ■) compared with placebo at Week 16 (Visit 8). As this trial is exploratory in nature, no adjustments for multiplicity will be made.

To assess the treatment effect at Week 16, change from baseline in average daily time (**minutes**) to first prodromal symptom associated with exposure to sunlight between 1 hour post sunrise and 1 hour pre-sunset at Weeks 2, 4, 6, 8, 10, 12, 14 and 16 will be analyzed using mixed-effect model for a repeated measures (MMRM). The model will include fixed categorical terms for treatment, the baseline average daily sunlight exposure time without prodromal symptoms (≤ 30 min or >30 min), visit, and treatment by visit interaction together with continuous covariate terms for baseline average daily duration of sunlight exposure between 1 hour post sunrise and 1 hour pre-sunset without prodromal symptoms and baseline average daily duration of sunlight exposure between 1 hour post sunrise and 1 hour pre-sunset to first prodromal symptom by visit interaction. An unstructured correlation structure will be used to model the within-subject variance covariance errors. Should convergence of the model fail (due to the small numbers of subjects in this study), other variance-covariance matrices such as AR(1) correlation matrix will be used if appropriate. The Kenward-Roger approximation will be used to estimate the denominator degrees of freedom. From the model described above, adjusted (least squares [LS]) means and standard errors will be produced by treatment and visit. Difference in adjusted means at each visit (each MT-7117 dose vs. placebo) with standard errors, 95% CIs and associated P-values will also be produced. All available data from all subjects will be used in the primary analysis without any imputation.

A supportive analysis will be performed in a similar manner for the primary endpoints using the PP set.

Non-parametric analysis will be performed in order to confirm the robustness for the above parametric model. The analysis will be carried out using Wilcoxon's rank sum test. The data of change from baseline in average daily duration (hours) of sunlight exposure between 1 hour post sunrise and 1 hour pre-sunset without prodromal symptoms at each visit/timepoint (Weeks 2, 4, 6, 8, 10, 12, 14 and 16) from two treatments being compared will enter the corresponding analysis. In addition, the point estimates and two-sided 95% confidence intervals for the difference between the treatment groups will be obtained using the Hodges-Lehman estimator.

10.2.2.2 Analysis of Secondary and Other Efficacy Endpoints

The detail of analysis method for secondary and other efficacy endpoints will be described in the SAP. The detail model for each endpoint will be described in the SAP.

The following secondary and other efficacy endpoints will be analyzed using the MMRM similar to the analyses for the primary endpoint.

- Change from baseline in average daily duration (**minutes**) of sunlight exposure between 1 hour post sunrise and 1 hour pre-sunset without prodromal symptoms.
- Change from baseline in average daily mean duration (**minutes**) of sunlight exposure between 1 hour post sunrise and 1 hour pre-sunset without prodromal symptoms. The daily mean duration is considered as multiple periods of sunlight exposure in each day and measurable by sum of duration of each period divided by number of periods.
- Change from baseline in average daily duration (**minutes**) of prodromal symptoms during 16-week double-blind treatment period.
- Change from baseline in average daily duration (**minutes**) of pain events during 16-week double-blind treatment period.
- The average daily mean intensity of the subject's prodromal symptoms during 16-week double-blind treatment period.
- The average daily mean intensity of the subject's pain events during 16-week double-blind treatment period.
- Change from baseline for all total score and total score in each domain of physical function, anxiety, depression, fatigue, sleep disturbance, ability to participate in social roles and activities, pain interference, pain intensity in PROMIS-57.
- PGIC.

The following endpoints will be analyzed; a negative binomial regression model with log link will be fitted. The model will include treatment as fixed effect, and baseline total number of sunlight exposure episodes with prodromal symptoms as the covariate. The estimated incidence rate (IR) and its 95% confidence interval for each treatment group, incidence rate ratio (IRR) of each active MT-7117 treatment group versus placebo, 95% confidence interval of the IRR together with relevant p-values will be reported.

- Total number of sunlight exposure episodes with prodromal symptoms during 16-week double-blind treatment period.
- Total number of pain events during 16-week double-blind treatment period.

The following secondary endpoint will be listed and summarized by treatment and planned time point using descriptive statistics. The value of melanin density, change from baseline and % change from baseline in melanin density at Week 8, 16 and 22 by skin segments and average of 6 skin segments will be plotted by treatment. For average of 6 skin segments for the value of melanin density, change from Baseline in melanin density at Week 8, 16 and 22, will be analyzed using MMRM similar to the analyses for the primary endpoint.

- The change from baseline and % change from baseline in melanin density at Week 8, 16, and 22 by skin segments. Average of 6 skin segments for the change from Baseline and % change from baseline in melanin density at Week 8, 16, and 22.

The following endpoint will be analyzed using ANCOVA or ANOVA model:

- Change from baseline in average daily duration (minutes) of sunlight exposure between 1 hour post sunrise and 1 hour pre-sunset on Saturday without prodromal symptoms at Week 16.
- Change from baseline for in-clinic sunlight exposure time (minutes) to the first prodromal symptoms
- Total time (hours) during 16-week double-blind treatment period in duration of sunlight exposure between 1 hour post sunrise and 1 hour pre-sunset without prodromal symptoms.
- Change from baseline in average daily duration of sunlight exposure regardless of time of day without prodromal symptoms assessed at Week 16.

The following endpoints will be summarized using descriptive statistics and Wilcoxon's rank sum test.

- Total number of days the subject is exposed to sunlight for any duration between 1 hour post sunrise and 1 hour pre-sunset without prodromal symptoms during 16-week double-blind treatment period.

10.2.3 Safety Assessments

Adverse Events

AEs are considered as treatment-emergent if they occur after the first dose administration of study drug or if a pre-dose event increases in severity following dosing.

AEs will be assumed to be treatment-emergent, unless there is clear evidence (if necessary through comparison of partial dates) to suggest that the AE started prior to the first dose of IMP.

The frequency and incidence of treatment-emergent AEs (TEAEs) will be summarized by system organ class (SOC) and preferred term (PT) by treatment period and overall. Summaries will also be produced by relationship to study drug and by maximum severity. The summary will be sorted by International Agreed Order for SOC and alphabetical order for preferred term (or by frequency from the highest to the lowest).

The following summaries will be presented:

- Summary of TEAEs by SOC and PT.
- Summary of TEAEs by SOC, PT and severity.
- Summary of TEAEs by SOC, PT and relationship.
- Summary of Serious TEAE by SOC and PT.
- Summary of TEAE leading to drug withdrawn by SOC, PT.

For each of the summaries produced at the subject level, multiple occurrences of the same event within a subject will be counted once in the summaries by SOC and preferred term; multiple occurrences of the same event within a subject will be counted once in the maximum severity category (severe > moderate > mild) and/or maximum study drug

relationship category (reasonable possibility/no reasonable possibility). If severity or relationship is found to be missing, the most severe occurrence will be imputed for that particular summary.

Safety laboratory tests

Routine laboratory safety tests include hematology, coagulation, biochemistry and urinalysis.

Continuous laboratory parameters will be summarised by scheduled time point and treatment group. Observed values as well as changes from baseline (Day -1) will be summarized by treatment groups. Categorical parameters will be summarized by frequency counts and percentages of subjects within each category.

The laboratory data will be listed in full with clinically relevant values flagged (L=Lower than normal range, H=Higher than normal range or A=Abnormal if no reference range).

The number of subjects with post baseline assessments \geq x3 ULN and \geq x5 ULN and so on will be calculated for ALT, AST, GGT, ALP, direct and total bilirubin and summarized by treatment for each post baseline visit.

Vital signs and electrocardiogram data

Vital signs and 12-lead ECG variables and changes from baseline will be descriptively summarized at each visit by treatment.

The baseline for the vital sign parameters and 12-lead ECG measurements will be the last valid assessment obtained on Day 1 prior to the administration of double-blind treatment period.

Physical examination and Nevi evaluation

For physical examination, the frequency and percentage of subjects with abnormal physical examinations will be summarized at each time point by body system and treatment.

Nevi assessment will be summarized in table by treatment with frequency and percentage for subjects' suspicious nevi found.

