Dose-proportional increases in systemic exposure based on AUC and C_{max} were observed over the single dose range of [redacted] to [redacted]. Following multiple doses at [redacted], [redacted], [redacted], and [redacted] MT-7117 was rapidly absorbed with median t_{max} values ranging from 4 to 5 hours post-dose on both Day 1 and Day 14. Mean $t_{1/2}$ values ranged from 6.28 to 15.55 hours on Day 1 and 10.56 to 18.97 hours on Day 14. Systemic exposure to MT-7117 in plasma, based on calculation of AUC and C_{max} , appeared to increase in a slightly more than dose-proportional manner over the [redacted] to [redacted] dose range. Steady-state was generally reached by 5 days of multiple dosing.

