3. STUDY DESIGN

3.1 Overall Study Design

This is a Phase II, randomized, double-blind, placebo-controlled study to assess the efficacy, tolerability, and safety of MT-7117 in subjects with EPP. The study consists of a 2-week screening period, a 16-week double-blind treatment period, and a 6-week follow-up period at Week 22. The total participation period is approximately 24 weeks.

This study is being conducted without regard to seasonality.

The study design is illustrated in Figure 3.1-1.

Subjects will attend Screening (Visit 1) up to 2 weeks before Randomization (Visit 2), in order to confirm eligibility and obtain pre-study safety assessments including nevi evaluation. Subjects will also be instructed how to use a sunlight exposure diary.

At Visit 2, subjects meeting eligibility criteria will be randomized in a 1:1:1 ratio to receive either [REDACTED], [REDACTED] of MT-7117, or matching placebo in a double-blind manner. Baseline average daily sunlight exposure time without prodromal symptoms (≤ 30 min and >30 min) will be used as stratum for the randomization. The first dose will be administered at Visit 2 following baseline assessment including in-clinic sunlight exposure test. Active or placebo [REDACTED] will be administered once daily in the morning with food.

Subjects will attend in-clinic visits at Weeks 4, 8, and 12 (Visits 5, 6, and 7, respectively) during which assessments will be performed. In addition, subjects will undergo mobile laboratory sample collection at Weeks 1 and 2 (Visits 3 and 4, respectively) to measure liver function markers (AST, ALT, GGT, ALP, direct and total bilirubin).

Subjects will attend the end of treatment visit at Week 16 or early termination (Visit 8). Following the last treatment visit, subjects will attend a follow-up visit at Week 22 or 6 weeks after early termination.

[figure not shown]

Figure 3.1-1 Study Design Schematic

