8. ADVERSE EVENT MANAGEMENT

All AEs and SAEs will be recorded in the source documents. All AEs and SAEs that occur from the time written informed consent is obtained until the end of the follow-up period (6 weeks after the last treatment visit, for safety monitoring) will be recorded in the eCRF.

ICF signing will occur weeks in advance of the first clinic visit (Visit 1), to account for subjects traveling long distances; these subjects will be required to sign the ICF before he or she travels to the clinic. In addition, there will be a provision for a pre-screening ICF in order to enable Visit 1 to align directly with the official study consent; however, the Sponsor safety team will determine when to officially collect AE.

Even if the AE is assessed by the Investigator as not related to study medication, its occurrence must be recorded in the source documents and eCRF. AEs will be classified as occurring at 'Baseline' if they occur before the administration of study medication. AEs will be classified as 'treatment-emergent' if they arise following the first administration of study medication in the double-blind treatment period (after randomization) or if a pre-dose AE increases in severity following dosing in the double-blind treatment period (after randomization).

At each study visit, after the subject has had an opportunity to spontaneously mention any problems, the Investigator or designee should inquire about the occurrence of AEs. The questioning should be open-ended and non-leading to avoid notifying either the subject or study site personnel of the actual treatment being administered.

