## 2.4 Safety Endpoints

### 2.4.1 Adverse events (AEs)

An AE is any untoward medical occurrence in a subject or clinical investigation subject administered a pharmaceutical product that does not necessarily have a causal relationship with this treatment.

AEs will be coded using Medical Dictionary for Regulatory Activities (MedDRA) central coding dictionary, Version 22.0 .

Treatment-emergent AEs (TEAEs) are defined as AEs that newly occurred or worsened in severity on or after the first dose of study double-blinded (DB) treatment. The treatment relationship with the AE is in 2 categories (reasonable possibility, no reasonable possibility). The detail is included in protocol.

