## 7.12 Safety Assessments

### 7.12.1 Adverse Events

The treatment emergent adverse events (TEAEs) are defined as AEs that newly occurred or increased in severity on or after the first dose of study medication.

The hepatic AEs will be selected from available TEAEs reviewed by the Clinical and Drug safety team. Then Clinical and Drug safety team will provide a list of hepatic AEs in Excel format to Data Science team. The list on Excel format will be used with clinical database to generate the hepatic AE table and listing.

The TEAEs are summarized for subjects with at least one TEAE, at least one treatment emergent adverse reaction, at least one serious TEAE, at least one serious treatment emergent adverse reaction, at least one TEAE leading to drug withdrawn, at least one treatment emergent adverse reaction leading to drug withdrawn, at least one hepatic AE, at least one Adverse Events of Special Interest (AESI) and fatal TEAE.

The frequency and incidence of TEAEs will be summarized by System Organ Class (SOC) and Preferred Term (PT) by treatment and overall. For this table, SOC is sorted by International order; then within SOC, PT is sorted by descending counts under MT-7117

Total group, then descending counts under Placebo group, then alphabetic order for PTs with the same count.

The AE summaries will be presented for the following:

- TEAEs by SOC and PT
- TEAEs by SOC, PT and severity
- TEAEs by SOC, PT and relationship
- Treatment emergent adverse reactions by SOC and PT
- Treatment emergent adverse reactions by SOC, PT and severity
- Serious TEAEs by SOC and PT
- Serious treatment emergent adverse reactions by SOC and PT
- TEAEs leading to drug withdrawn by SOC and PT
- TEAEs by SOC and PT for TEAEs with frequency  $\geq 3\%$  in total MT-7117 group
- Treatment Emergent Hepatic AEs by SOC and PT

For each of the summaries will be done at the subject level - multiple occurrences of the same event within a subject will be counted once in the summaries by SOC and PT; multiple occurrences of the same event within a subject will be counted once in the maximum intensity category (severe > moderate > mild) and/or maximum drug relationship category (reasonable possibility, no reasonable possibility). If intensity or relationship is found to be missing the most severe occurrence will be imputed for that particular summary.

All AEs for each subject, including multiple occurrences of the same event, will be listed.

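### The protocol plans adverse event summaries by treatment period; the SAP drops the period without saying so, so no between-arm table separates events that began on drug from those that began after it stopped

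*Protocol*

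**What the plan says.** **Tabulation.** Protocol 10.2.3 (Safety Assessments) says TEAEs "will be summarized by system organ class (SOC) and preferred term (PT) by treatment period and overall". SAP 7.12.1 (Adverse Events) reads: "The frequency and incidence of TEAEs will be summarized by System Organ Class (SOC) and Preferred Term (PT) by treatment and overall". The SAP then lists ten adverse event summaries, and none has a period dimension. SAP section 8 states that the protocol's analyses are unchanged.

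**Definition.** Protocol 10.2.3: "AEs are considered as treatment-emergent if they occur after the first dose administration of study drug". SAP 2.4.1: "AEs that newly occurred or worsened in severity on or after the first dose of study double-blinded (DB) treatment". Both give a start and neither gives an end.

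**Collection.** Under Protocol section 8, adverse events run from consent "until the end of the follow-up period (6 weeks after the last treatment visit, for safety monitoring) will be recorded in the eCRF".

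**Timeline.** Protocol 3.1 gives "a 16-week double-blind treatment period, and a 6-week follow-up period at Week 22" after a 2-week screening period.

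**The concern.** A subject whose first episode of an event comes in Week 21, five weeks after the last dose, is counted in the same table cell as one whose first episode comes in Week 3. The tables by arm therefore mix time on drug with time off drug, and the split that the protocol appears to plan is missing without a declared change.

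This matters because safety is part of the primary objective (Protocol 2.1.1) and the follow-up visit is there partly to judge safety and the recovery of pigmentation (Protocol 3.2). Whether an excess of events belongs to the dosing weeks or to the weeks after them is a question this trial should be able to answer by arm.

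The gap also stands out within the SAP. Diary data have a separate Week 22 window that must not overlap with treatment (SAP Table 4), and vital signs, laboratory tests and nevi are tabulated by visit. Adverse event summaries alone have no time dimension.

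**Working it through.** **1. Timeline.** The protocol's own total is reproduced: 2 + 16 + 6 = 24 weeks. Visit 8 is Day 113 and Visit 9 is Day 155, and 155 − 113 = 42 days = 6 weeks.

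**2. Share of post-dose time off drug.**
- Completer: 6/22 = 27.3%.
- Stops at Week 8, with follow-up 6 weeks later: 6/14 = 43%.
- Stops at Week 8 but stays on study to Week 22, which Protocol 4.5 allows: 14/22 = 64%.
- Allowing for washout: Protocol 1.5 reports mean half-lives of "10.56 to 18.97 hours on Day 14". Taking five half-lives as washout (an assumption), 5 × 18.97 / 24 = 4.0 days. Then 42 − 4 = 38 days, or 38/154 = 25% of post-dose time, have negligible plasma drug.

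**3. Effect on the arm comparison.** The documents give no adverse event rates in EPP, so the inputs here are assumptions: a constant placebo hazard, a hazard ratio (HR) of 2 on drug, and a range of placebo risks p over 16 weeks. Let S = 1 − p.

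- 16 weeks: placebo p; active 1 − S^2.
- 22 weeks, effect stops with the drug: placebo 1 − S^(22/16); active 1 − S^2 × S^(6/16). The risk difference (RD) is multiplied by S^(6/16).
- 22 weeks, effect persists through follow-up: active 1 − S^(2 × 22/16).

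For p = 10%, effect stopping with the drug:
- 16 weeks: 1 − 0.9^2 = 19.0% against 10.0%; RD 9.0 points, risk ratio (RR) 1.90.
- 22 weeks: 1 − 0.81 × 0.9^0.375 = 22.1% against 1 − 0.9^1.375 = 13.5%; RD 8.7 points, RR 1.64.

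| Placebo risk, 16 weeks | RD, 16 weeks | RD, pooled, effect stops | RR, 16 weeks | RR, pooled, effect stops | RD, pooled, effect persists |
|---|---|---|---|---|---|
| 5% | 4.8 | 4.7 | 1.95 | 1.68 | 6.4 |
| 10% | 9.0 | 8.7 | 1.90 | 1.64 | 11.7 |
| 20% | 16.0 | 14.7 | 1.80 | 1.56 | 19.4 |
| 40% | 24.0 | 19.8 | 1.60 | 1.39 | 25.0 |
| 60% | 24.0 | 17.0 | 1.40 | 1.24 | 20.3 |

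RD is in percentage points.

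**4. Reading the table.** If the effect stops with the drug, pooling lowers the risk ratio visibly at every background risk. It barely moves the risk difference for uncommon events: the 10% row loses about 0.3 points, or 0.1 subject in an arm of 34. The loss is 4.2 points at 40%. If the effect persists, pooling enlarges the risk difference at backgrounds of 5% to 40%. At 60% the difference still shrinks, because most subjects have already had the event. The direction therefore cannot be known in advance.

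**The case against.** **The split may never have been planned.** This is the strongest point. The trial is parallel-group with one treatment period, and follow-up is never called a treatment period. The same phrase appears for PK listings (Protocol 10.2.4, SAP 7.13), although PK samples are drawn only at Visits 2 and 5 to 8, so it may be template wording. The protocol sentence also omits a summary by arm, which the SAP supplies. This stands as a caution. The schedule of assessments, however, is headed by screening, double-blind treatment and follow-up, and a summary by period plus overall makes sense only if there are parts to combine. Either way the two texts differ and the SAP does not say so.

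**The open-ended definition is not the SAP's doing.** This stands. The protocol's definition has no end either, its own overall summary would pool in the same way, and collection stops at the end of follow-up. Protocol section 8 does mention the double-blind period when it defines treatment emergence, but that qualifies the dosing, not the onset of the event.

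**A reader might infer that pooling dilutes drug effects and charges off-drug events to the drug.** The documents do not support that as a general statement. Placebo follow-up events are pooled identically, and causality is a separate investigator judgement with its own tables. The skin events in the Phase I study showed only signs of reversing during its follow-up (Protocol 1.5), so some effects may well outlast plasma drug. The idea that sun reactions rebound once protection is lost is a hypothesis that no section states.

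**Timing is recoverable.** Every adverse event is listed, and SAP 5.4.8 derives the days from first dose to onset. That is true, but neither gives a comparison by arm, on drug and after.

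**Conclusion.** The mismatch between Protocol 10.2.3 and SAP 7.12.1 is real and undeclared. As written, every TEAE summary that counts onset through follow-up mixes 16 weeks on drug with 6 weeks off it, 27% of a completer's post-dose time and more for early stoppers. That the missing split is double-blind versus follow-up is an inference.

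The numerical effect is conditional on assumed background risks, a constant hazard and a hazard ratio of 2. It is small on the risk-difference scale for uncommon events, larger for common ones, and can reverse if effects persist. No test of adverse events is planned, so no formal conclusion turns on it.

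The case for change is that only columns by period show which situation applies. This is a cheap improvement, not a flaw that invalidates the safety analysis.

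**What to change.** In SAP 7.12.1:

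- Show the all, related, serious and hepatic TEAE tables by arm for (a) onset in the double-blind treatment period and (b) onset in follow-up, beside the existing overall column.
- Assign each event by its onset date against the subject's last dose date, so that time off drug after early stopping falls in (b). Where no last dose date is available, the SAP's own exposure convention (end-of-treatment visit date, SAP 5.4.10) could serve.
- If events shortly after the last dose are to count as on-drug, pre-specify that lag before unblinding. Do not simply fix it at the 4 days implied by plasma half-life, because pigment effects may last longer.
- Leave the table of TEAEs leading to drug withdrawal unsplit; those events are on drug almost by construction.

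In SAP section 8, reconcile the two wordings: say what the protocol's period means for adverse event tables or, if the split is not adopted, record the omission and the reason.

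The cost is SAP wording, some programming and longer tables. Onset dates are already recorded, and no new data collection is foreseen.
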